### **13.4 Primary Objective, Endpoint(s), Analysis Plan**

The primary objectives are to establish MTD, collect safety data of Polyphenon E/EGCG at MTD treatment in participants with cirrhosis and to determine the suppressing effects of /Polyphenon E/EGCG treatment on  $\gamma$ -hydroxy-1,N(2)-propanodeoxyguanosine ( $\gamma$ -OHPdG)levels in cirrhotic liver.

To assess the safety of Polyphenon E treatment in participants with cirrhosis, we will list all the adverse events and provide summary statistics.

To explore possible effects of Polyphenon E treatment on  $\gamma$ -OHPdG levels in cirrhotic liver samples of participants known to have high levels in liver biopsy samples.

The primary study objective is to assess the effect of Polyphenon E treatment on  $\gamma$ -OHPdG expression. Based on our preliminary data, we expect a 30-40% decrease in  $\gamma$ -OHPdG expression in cirrhotic liver after six months of Polyphenon E treatment. Twenty-four subjects with high  $\gamma$ -OHPdG levels in their liver biopsies will receive Polyphenon E. This provides 80% or greater statistical power to confirm a 30% or bigger decrease in  $\gamma$ -OHPdG levels at a 0.05 alpha level with a two sided test, and coefficient of variation = 50%-100%. We will use a nonparametric Wilcoxon test to compare the post-pre differences to zero. We anticipate that high pre-therapy IHC scores = 3, 4 and 5 vs. post-therapy scores mean = 2, —using a pre-therapy average of 4 to be conservative. Thus we will have two scores per person. The difference between Before and After = Before - After = B-A should be on average = 0 if treatment has no effect and on average about 1.33 and 1.60 after treatment = reduction of 33% and 40% respectively, down from 4.

Under usual assumptions of  $\text{corr}(B,A) = 0.5$  and  $SD(B) = SD(A)$  we get mathematically  $SD(B-A) = SD(B) = SD(A) = 2$ .  $SD=2$  was selected so as to give  $CV=100\%$  when  $mean = 2$  and  $CV=50\%$  when  $mean = 4$ .

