### **Numeric Results for Wilcoxon Test (Normal Distribution)**

Null Hypothesis:  $\text{Mean0}=\text{Mean1}$     Alternative Hypothesis:  $\text{Mean0}\neq\text{Mean1}$

Unknown standard deviation.

| Power   | N  | Alpha | Beta    | Mean0 | Mean1 | SD | Effect Size |
|---------|----|-------|---------|-------|-------|----|-------------|
| 0.84466 | 24 | 0.05  | 0.15534 | 0     | 1.33  | 2  | 0.665       |
| 0.94694 | 24 | 0.05  | 0.05306 | 0     | 1.6   | 2  | 0.8         |

Safety and adverse event data will be summarized using descriptive (frequency, %) statistics by dose cohort. The primary endpoint of MTD cannot be established because the study was closed early, and, based on the observed safety profile with a single DTC occurring in dose cohort 4 (1/4 patients), future studies can consider dose level 3 as the starting dose.

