### 13.5 Secondary Objectives, Endpoints, Analysis Plans

#### Secondary endpoints:

- a) To collect Polyphenon E/EGCG pharmacokinetic data in participants with cirrhosis.
- b) To determine the effects of Polyphenon E/EGCG treatment on the suppression of  $\gamma$ -hydroxy-1,N(2)-propanodeoxyguanosine ( $\gamma$ -OHPdG) levels in cirrhotic liver by LC-MS assay from baseline to post-treatment.
- c) To estimate the fraction of participants with liver cirrhosis that have high levels of  $\gamma$ -OHPdG.

We will test the  $\gamma$ -OHPdG levels at baseline and at the end of study in all subjects. Based on our preclinical models, we believe six months of intervention will decrease the  $\gamma$ -OHPdG levels. We will use two methods to measure the level of  $\gamma$ -OHPdG including IHC stain and Mass Spectrum analysis. The pathology slides prepared from the liver biopsy will be stained for antibody targeting  $\gamma$ -OHPdG. The level of  $\gamma$ -OHPdG will be scored from 0 to 6. IHC score of 0 to 2 is defined as  $\gamma$ -OHPdG low, and IHC score of 3 to 6 is defined as  $\gamma$ -OHPdG high. When  $\gamma$ -OHPdG is measured by mass spectrum, the absolute amount of  $\gamma$ -OHPdG will be measured. In this study, we hope to evaluate whether decrease in  $\gamma$ -OHPdG level will result in decrease in mutation frequency only in five subjects due to budget restriction. The data will help to test our hypothesis and support future studies. If there is no restriction in budget, we would like to carry out the study in all subjects.

For secondary outcome (b) LC-MS assay will be used to determine gamma-OHPdG changes from baseline to post-treatment. This will generate a continuous variable for values of gamma-OHPdG. Descriptive statistics (mean, range) will be used to summarize this continuous outcome by dose level. A nonparametric trend test will be used to examine whether there is a trend for greater reduction in gamma-OHPdG as the dose level increases.

For secondary outcome (c) we will use descriptive statistics to estimate the fraction of participants with liver cirrhosis that have high levels of  $\gamma$ -OHPdG. Participants will be screened for high levels of  $\gamma$ -OHPdG. Only participants with high levels of  $\gamma$ -OHPdG will be enrolled for intervention. The

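### Section 13.4 claims at least 80% power for a 30% decrease, but the table starts at 33% with one SD of 2; its own method gives 77% at 30%, and the CV range is not a range of variability

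*Combined protocol and SAP*

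**What the plan says.** Section 13.4 plans a two-sided Wilcoxon test of the paired pre/post IHC differences against zero, "at a 0.05 alpha level with a two sided test". For the 24 treated subjects it states: "This provides 80% or greater statistical power to confirm a 30% or bigger decrease" in γ-OHPdG, with "coefficient of variation = 50%-100" percent.

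The inputs follow in the same section. The baseline mean is taken as 4. The expected scores are given as: "We anticipate that high pre-therapy IHC scores = 3, 4 and 5 vs. post-therapy scores mean = 2". The effects carried into the calculation are differences of 1.33 and 1.60, labelled 33% and 40% of 4. With a before/after correlation of 0.5 and equal SDs, SD(B-A) is set to 2. The text explains that 2 was chosen because it is a CV of 100% at a mean of 2 and of 50% at a mean of 4.

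The table that follows has two rows, both with N = 24 and SD = 2: power 0.84466 for 1.33 ("0.84466 | 24 | 0.05") and 0.94694 for 1.60.

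Section 13.5 gives the scale as 0 to 6, "and IHC score of 3 to 6 is defined as" high. Inclusion criterion 4.1.7 admits to treatment only participants scoring 3 or more.

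**The concern.** The sentence and the table do not match. The sentence names a 30% decrease and a span of CVs. The table has no 30% row and one SD. Thirty percent is also the lower end of the 30-40% decrease that the section expects, so it is the case that a reader would most want covered.

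Three further inputs do not fit together. A CV of 50%-100% reads as variability over which the power was checked, but only one SD entered the calculation. A post-therapy mean of 2 is a 50% drop from 4, which is neither of the effects used. And the SD assumed at baseline has to be possible for people selected to score 3 to 6.

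This is the only power statement for the primary biomarker test. Section 13.1 reports that enrolment stopped at 13 with 10 pre/post pairs, yet the 24-subject statement stands unqualified. A reader who relied on it could take a non-significant result as stronger evidence against an effect than it is.

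**Working it through.** **Inputs, all from 13.4 unless noted.** Two-sided alpha 0.05; N = 24 pairs; baseline mean 4; SD(B) = SD(A) = 2; correlation 0.5; eligible baseline scores 3 to 6 (4.1.7 and 13.5).

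**1. SD of the difference.** SD(B-A) = √(SD(B)² + SD(A)² − 2 × 0.5 × SD(B) × SD(A)) = √(4 + 4 − 4) = 2, as stated.

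**2. Reproduce the table.** Reduce N by the efficiency of the Wilcoxon test relative to the t-test for normal data: 24 × 3/π = 22.9, truncated to 22. Then use one-sample noncentral-t power with n = 22 and effect size = difference / SD.

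| Difference | Effect size | Power, recomputed | Power, table |
|---|---|---|---|
| 1.33 | 0.665 | 0.84466 | 0.84466 |
| 1.60 | 0.80 | 0.94694 | 0.94694 |

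Both agree to five decimals, so this is taken as the table's method.

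**3. The missing 30% row.** A 30% decrease is 0.30 × 4 = 1.20, an effect size of 1.20/2 = 0.60.

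| Calculation, N = 24 | Power at 30% |
|---|---|
| Table's method (n = 22) | 76.5% |
| Same, without truncation (n = 22.9) | 78.4% |
| Exact Wilcoxon, simulated | 78-79% |
| Paired t-test (not the planned test) | 80.4% |

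By the table's method, 80% power needs an effect size of 0.626. That is a difference of 0.626 × 2 = 1.25, or 1.25/4 = 31.3%. At a 30% decrease, 80% power needs 26 pairs.

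**4. The CV range.** 2/4 = 50% and 2/2 = 100%: one SD over two means. The second mean is a (4 − 2)/4 = 50% decrease. The effects in the table leave post-therapy means of 4 − 1.33 = 2.67 and 4 − 1.60 = 2.40. A 30% decrease leaves 2.80, where an SD of 2 is a CV of 2/2.80 = 71%.

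**5. Can the baseline SD be 2?** For scores between 3 and 6 with mean 4, the largest possible SD is √((6 − 4)(4 − 3)) = 1.41. So SD(B) = 2 cannot occur in the eligible population.

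**6. What that does to power.** Keep the correlation of 0.5 and put SD(B) at its ceiling of 1.41. Power is by the table's method at a 30% decrease:

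- SD(A) = 1.41: SD(B-A) = √(2 + 2 − 2) = 1.41, effect size 0.85, power 97%.
- SD(A) = 2: SD(B-A) = √(2 + 4 − 2.83) = 1.78, effect size 0.67, power 85%.
- SD(A) at its own ceiling for a mean of 2.8 on the 0-6 scale, √(2.8 × 3.2) = 2.99: SD(B-A) = √(2 + 8.96 − 4.23) = 2.59, effect size 0.46, power 54%.

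Power at 30% reaches 80% when SD(B-A) is about 1.92 or less. Correcting the baseline SD can therefore raise the power above the claim. It falls short only if post-therapy scores vary more than planned.

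**The case against.** The strongest reply is that the gap is trivial. By untruncated or exact Wilcoxon calculation it is 1.6 points or less, and the 80% threshold sits at about 31% rather than 30%, so the sentence has in effect rounded 33% down to 30%. The bound on the baseline SD also suggests that 2 may be conservative. With 10 pairs obtained, the 24-subject calculation no longer governs any decision, and section 13.5 already says that estimates will carry 95% confidence intervals.

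Most of this stands. It limits the size of the point, but it does not supply a 30% row or a second SD, and it does not make SD(B) = 2 possible.

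A reader might go further and infer that the plan claims 80% power at a baseline CV of 75% or 100%, that is an SD of 3 or 4 at a mean of 4, and that the claim collapses there. The documents do not support this. Section 13.4 ties the CV of 100% to a mean of 2, with the SD still 2. The eligibility floor rules out a baseline SD of 3 or 4 in any case. A reader might also infer from the impossible baseline SD that the study was underpowered. Step 6 shows that this does not follow.

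**Conclusion.** The claim of at least 80% power at a 30% decrease is not delivered by the calculation given for it. At N = 24 and SD(B-A) = 2, power is 77% by the table's method and 78-79% by simulated exact Wilcoxon, a shortfall of about 1 to 3.5 points. It rests on normally distributed differences and on SD(B-A) = 2.

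Two supporting statements fail independently of that figure. The CV range describes one SD in two ways, so power was shown over no range of variability, and its anchor at a mean of 2 does not match the 33% and 40% effects. The derivation of SD(B-A) = 2 from SD(B) = 2 cannot hold for baseline scores of 3 to 6 with mean 4.

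Whether the true power at 24 pairs would have been above or below 80% cannot be settled from the documents, because they give no data on the SD of the change. This is a small, conditional error in a stated power and is worth correcting.

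**What to change.** In 13.4, replace the power sentence with: *With 24 pairs and an assumed SD(B-A) = 2, power is 77%, 84% and 95% for decreases of 30%, 33% and 40%.* Delete the CV range and the post-therapy mean of 2. Either label SD(B-A) = 2 as an assumption, or re-derive it from baseline scores limited to 3-6 and note that power could then be higher.

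Add that this calculation does not apply to the 10 pairs obtained, and that the primary biomarker result will be reported as the estimated change with its 95% confidence interval. Section 13.5 already makes a general commitment to such intervals, so this only ties it to the primary analysis.

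The cost is a few lines of text. No procedure, sample or analysis changes. At SD(B-A) = 2 the stated power for a 30% decrease becomes slightly less favourable.

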HCC animal model data support the ability of  $\gamma$ -OHPdG levels to predict the development of HCC. In addition,  $\gamma$ -OHPdG levels have been shown to correlate with GC to AT mutations, and other mutations in oncogene and tumor suppressor genes found in human HCC, which supports the mechanistic role of  $\gamma$ -OHPdG in hepatocarcinogenesis. In our preliminary study, we found that 38% of 68 cirrhotic liver samples expressed high level of  $\gamma$ -OHPdG. In order to test  $\gamma$ -OHPdG as a predictive biomarker for HCC development, we first need to collect additional data on the prevalence of high  $\gamma$ -OHPdG levels (IHC score of 3 or higher) in liver cirrhosis, the stability of  $\gamma$ -OHPdG levels during the course of cirrhosis, and the correlation of high  $\gamma$ -OHPdG levels (IHC score of 3 or higher) with the development of HCC. In this phase I study, secondary endpoints were chosen to estimate the fraction of participants with liver cirrhosis that have high levels of  $\gamma$ -OHPdG, and the stability of the  $\gamma$ -OHPdG marker over time in each individual. In addition, we will also test the effect of EGCG on the level of liver stiffness as measured by FibroScan® and FIB-4 score as an exploratory study endpoint. We will also develop an LC-MS and/or ELISA-based method for detecting urinary  $\gamma$ -OHPdG as an exploratory study endpoint. Lastly, it is unlikely that a patient will develop HCC during the short time they are on study. However, we will measure the incidence of HCC across all dosage levels, and have thus added it as an exploratory endpoint.

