## 4. PARTICIPANT SELECTION

### 4.1 Inclusion Criteria

4.1.1 Participants with a clinical diagnosis of cirrhosis based on the investigators evaluation, confirmed by ANY ONE of the three following methods to define cirrhosis:

- Established cirrhosis on liver biopsy (METAVIR F4);
- Ultrasound, CT or MRI findings consistent with cirrhosis. Nodular appearing liver with or without evidence of portal hypertension

- Transient elastography (FibroScan) with a result  $> 12.5$  kPa  
Etiology of cirrhosis will not be considered in determining inclusion in the study.

4.1.2 Participant is able and willing to comply with study procedures, and signed and dated informed consent is obtained.

4.1.3 Participant agrees to consume no more than 2 cups of green tea per day and refrain from taking supplements or foods labeled as containing green tea.

4.1.4 Participant must be aged  $\geq 18$  years. Because no dosing or adverse event (AE) data are currently available on the use of Polyphenon E in participants  $< 18$  years of age, children are excluded from this study but will be eligible for future pediatric trials, if applicable.

4.1.5 ECOG performance status  $\leq 1$  (Karnofsky  $\geq 70\%$ ; see Appendix A).

4.1.6 Participants must have adequate organ and marrow function as defined below in Table 2:

Table 2:

| System  | Laboratory Value  |
|---|---|
| Hematological  |   |
| Platelets   | $\geq 75,000 / \mu\text{L}$   |
| Hemoglobin  | $\geq 8 \text{ g/dL}$   |
| Renal function   |   |
| Serum creatinine OR
Measured or calculated a creatinine clearance
(GFR can also be used in place of creatinine or CrCl) | Within normal institutional limits OR
GFR within normal institutional limits as adjusted for age and sex. |
| Hepatic function   |   |
| Serum direct bilirubin  | Within normal institutional limits  |
| AST (SGOT) and ALT (SGPT)   | $\leq 2.5 \times \text{UNL}$  |
| Albumin   | $\geq 3.0 \text{ g/dL}$   |
| Coagulation  |   |
| International Normalized Ratio (INR)  | $\leq 1.3$  |
| Other  |   |
| Ascites   | Absent  |
| Encephalopathy  | Absent  |

4.1.7 Only participants found to express high levels (IHC score 3 and above) of  $\gamma$ -OHPdG ( $\gamma$ -OHPdG-high HCC) in baseline or archival liver biopsy will be registered to receive Polyphenon E treatment.

4.1.8 Participant is able to undergo radiographic evaluation with ultrasound, CT or MRI.

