## **6.9 Blinding and Unblinding Methods**

This trial is a single-arm, open-label study.

DCP Medical/Task Order Monitor  
[name] [name], FACS  
NCI/Division of Cancer Prevention  
[name]  
[name]  
[name]  
[contact]  
[contact]  
Email: [[contact]](mailto:[contact])

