Our preliminary data shows that  $\gamma$ -OHPdG predicts HCC development. Among the 3 anti-oxidants—Theaphenon E, lipoic acid, and vitamin E—used in 3 HCC animal models, only Theaphenon E effectively suppressed the accumulation of  $\gamma$ -OHPdG and prevented HCC development. Theaphenon E contains the same active components—epigallocatechin gallate (EGCG), epigallocatechin (EGC), and epicatechin (EC)—as the dietary antioxidant, Polyphenon E. EGCG has been tested in many clinical cancer prevention trials. We propose that the accumulation of the DNA adduct,  $\gamma$ -OHPdG, predicts the development of HCC, and that Polyphenon E suppresses the formation of  $\gamma$ -OHPdG, which may reduce HCC development in participants with cirrhosis. In this pilot study, our primary endpoint is to determine the effect of EGCG treatment on  $\gamma$ -OHPdG levels in cirrhotic liver. During screening, subjects will have a baseline biopsy taken. Only subjects found to have high  $\gamma$ -OHPdG levels (IHC score equal or higher than 3) in their cirrhotic liver will receive EGCG treatment for 24 weeks. An exit liver biopsy will be taken at the end of intervention and will be compared with the baseline biopsy for changes in liver  $\gamma$ -OHPdG levels. All liver tissue slides from the biopsy will be processed and stained with an anti-  $\gamma$ -OHPdG antibody in the lab of [name]. Two pathologists: [name] from GU and [name] [name] from UPR will review the slides and score the level of  $\gamma$ -OHPdG in the participant liver biopsy samples.

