fraction of participants with liver cirrhosis that have high levels of  $\gamma$ -OHPdG is calculated based on the number of subjects enrolled over the number of subjects screened based on the levels of  $\gamma$ -OHPdG in their first liver biopsy. This important information may help to estimate the portion of cirrhotic participants with high risk for HCC development, and can be used to design a future large chemoprevention study using Polyphenon E or other green tea extract in HCC prevention.

Due to the early stopping, secondary and exploratory endpoints will be summarized using descriptive statistics across dose cohorts. Changes in biomarkers across dose levels will be analyzed using a nonparametric trend test.

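### In a single-arm trial that treats only patients with a high baseline IHC score, zero is not the no-effect value for the change: selection alone shifts the estimate towards suppression, probably modestly

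*Combined protocol and SAP*

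**What the plan says.** **Selection.** Section 4.1.7 begins "Only participants found to express high levels (IHC score 3 and above" and admits such patients on a baseline or an archival biopsy. Section 13.5 sets the scale at 0 to 6, where "IHC score of 3 to 6 is defined as" high.

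**Comparison.** Section 8.1.2: "An exit liver biopsy will be taken at the end of intervention and will be compared with the baseline biopsy for changes in liver" γ-OHPdG. Section 6.9: "This trial is a single-arm, open-label study".

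**Test.** Section 13.4: "We will use a nonparametric Wilcoxon test to compare the post-pre differences to zero", two-sided at 0.05, sized for 24 treated patients. Its stated null is that "B-A should be on average = 0 if treatment has no effect", where B is Before and A is After.

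**Existing caution.** Section 13.6 promises a note that results could be biased by a background change over time unrelated to treatment. Regression to the mean is not mentioned anywhere.

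**After early stopping.** Section 13.1 (Table 6) reports 13 treated patients in four dose cohorts, 10 of them with paired biopsies, and no expansion cohort. Section 13.5 adds: "Due to the early stopping, secondary and exploratory endpoints will be summarized using descriptive statistics across dose cohorts". It then plans a nonparametric trend test of biomarker change across dose levels.

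**The concern.** The same biopsy reading selects the patient and serves as Before. Patients who pass a cut at 3 include some whose reading was high by chance, through where the needle fell, how the slide was read, or short-term fluctuation. Their next reading is lower on average with no treatment at all. With no untreated group, a test against zero credits this fall to Polyphenon E.

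Suppression of γ-OHPdG is a primary objective, and Section 9.1 says the pilot data will support a larger study. An uncorrected fall would overstate the effect used to plan that study.

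**Working it through.** **1. The plan's own figures.** With SD(B) = SD(A) = 2 and correlation 0.5, SD(B-A) = sqrt(4 + 4 - 2 x 0.5 x 4) = 2. The effect sizes are 1.33/2 = 0.665 and 1.6/2 = 0.8. Reducing N by the Wilcoxon efficiency gives 24 x 3/π = 22.9, truncated to 22. Noncentral-t power is then 0.84466 and 0.94694, exactly as printed in Section 13.4. The arithmetic is right; the question is the null value.

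**2. Expected B-A with no drug effect.** The share scoring high is 26/68 = 0.382 (Section 2.3.4). Assumptions not in the documents: bivariate normal scores, population SD 2, equal means at both times, and a cut at 2.5 on the underlying scale (integer scores of 3 or more).

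- Normal deviate for the upper 38.2%: 0.299. Population mean: 2.5 - 0.299 x 2 = 1.90.
- Density over tail area: 0.998. Treated mean: 1.90 + 0.998 x 2 = 3.90, close to the plan's 4.
- Expected B-A = (1 - rho) x (treated mean - population mean) = (1 - rho) x 1.995.

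**3. Fit to the serial biopsies.** Section 2.3.5 reports that all 14 evaluable pairs stayed in the same category. The chance of this is the same-category probability to the power 14, treating the pairs as random draws with 38% high.

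**4. Error rate with 10 pairs.** Simulated integer scores of 0-6, no drug effect, rejection in the suppression direction (nominal 2.5%).

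| | rho 0.8 | rho 0.9 | rho 0.95 |
|---|---|---|---|
| Expected B-A (points) | 0.40 | 0.20 | 0.10 |
| Share of 1.33 | 30% | 15% | 8% |
| Same category, one pair | 0.804 | 0.863 | 0.903 |
| Chance of 14 of 14 | 4.8% | 13% | 24% |
| Exact test | 9.1% | 3.8% | 1.6% |
| Normal approximation | 15.0% | 8.9% | 7.1% |

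Counting both directions, the exact test rejects 9.1%, 3.9% and 1.6% of the time (nominal 5%).

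**5. Sensitivity.** With population SD 1.5 the shifts are 0.30, 0.15 and 0.07. With the 30% high rate in Section 9.2 they are 0.46, 0.23 and 0.12.

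**The case against.** **Stability has been studied.** The end of Section 2.3.6 calls levels relatively stable, and Section 13.10 says stability has been studied. A reader of Section 2.5.3 alone might infer that it is wholly unproven: that section says more data are needed and lists as a secondary endpoint the stability of the "marker over time in each individual", which Sections 1.2 and 13.5 do not carry forward. Taken together, the documents are mixed. The stability result limits the bias but cannot show it is zero, because the text of 2.3.5 reports only category membership. Numeric scores may be in the figure it cites, which was not available here.

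**The test may be moot.** It was sized for 24 patients, a number tied to an expansion that never opened. A reader might infer that the test certainly stands because only secondary and exploratory endpoints were made descriptive, or that the trend test replaced it. Neither is stated. The test is not withdrawn, and its status is unclear. The trend test is less exposed, since the selection shift should be similar across doses.

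**The plan's correlation of 0.5 implies more.** Read as the correlation among treated patients, it corresponds to about 0.72 before selection and a shift of 0.55 points. But Section 13.4 offers 0.5 as a usual assumption, not an estimate, and at 0.72 the chance of 14 of 14 is 2.5%.

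**Other safeguards.** Two pathologists and the LC-MS assay reduce reading and assay error. LC-MS uses portions of the same liver sample, so sampling error in the selecting biopsy remains. A rise in untreated levels, as seen with age in mice (Section 2.5.1), would offset the bias; the plan does not show one in patients.

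**Conclusion.** The no-effect statement in Section 13.4 is wrong unless untreated scores repeat perfectly or levels rise over time. The direction of the bias follows from the design. Its size does not: it rests on the assumptions in the working, and the normal model with SD 2 is only approximate on a 0-6 scale. The range best supported by the 14 serial pairs is about 0.1 to 0.2 points, or 8-15% of the design effect. A shift of 0.4 points (30%) is possible but fits those pairs less well.

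A reader might infer a seriously inflated false-positive rate. At 24 patients the same simulation gives 35%, 17% and 9% for rho 0.8, 0.9 and 0.95, but that design was not reached. With 10 pairs and an exact test on integer scores, the rate stays below 5% at rho 0.9 or more, so the main harm there is the biased estimate. The normal approximation does not keep it there, so the version of the test matters. Nor do the documents support reading any observed fall as wholly an artefact. This should be fixed before the IHC change is reported.

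**What to change.** - **Section 13.4:** state that B-A averages zero without an effect only if untreated scores are perfectly repeatable and stable.
- **Reporting:** beside the mean IHC change and its 95% CI (Section 13.5 already promises intervals), show the shift expected from selection, (1 - rho) x (mean of treated minus mean of all screened). Use the screening scores, low and high, already collected for objective 1.2.3. Show rho 0.8, 0.9 and 0.95, or estimate rho from the 14 serial pairs if their numeric scores are available.
- **Section 13.6:** name regression to the mean. State whether the Wilcoxon test against zero is still to be run on the 10 pairs, and whether in exact or normal-approximation form. State that its p-value cannot by itself be attributed to the drug.
- **Before:** Section 7.1 (footnote j) allows an optional fresh Screen 2 biopsy when archival tissue exists, and the plan does not say which is Before. Where archival tissue decided eligibility and a fresh biopsy exists, use the fresh one, which did not select the patient, and report how many patients this affects.

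The cost is wording and one small table from scores already held; no new patients, biopsies or assays. The downside is that rho is imprecise. With 14 pairs, an observed 0.9 has a 95% CI of tanh(1.472 ± 1.96/sqrt(11)), or 0.71 to 0.97. The shift is therefore a range and not a corrected test, and the headline change will look less favourable.

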#### **2.3.4 $\gamma$ -OHPdG is elevated in human cirrhotic liver compared with normal liver.**

The data described above demonstrates that  $\gamma$ -OHPdG is closely associated with liver carcinogenesis in animal models. To investigate the role of  $\gamma$ -OHPdG in human HCC, 40 human liver samples were procured with different pathologies/diagnoses, including 2 normal livers, 7 livers with cirrhosis, 4 with hyperplasia, 3 with cirrhosis and hyperplasia, and 22 with HCC. Samples were stained with a  $\gamma$ -OHPdG monoclonal antibody developed in our laboratory (49). The association between pathology and expression level of  $\gamma$ -OHPdG was examined using Fisher test. A significant association was found between liver disease progression and the immunoscore of  $\gamma$ -OHPdG with  $p = 0.0364$ . However, the immunoscore of  $\gamma$ -OHPdG was not associated with the stages of HCC ( $p = 0.3259$ ).

We then further characterized  $\gamma$ -OHPdG adduct levels in participants with cirrhosis (an advanced stage of liver disease preceding HCC development). Sixty-eight human liver biopsy samples from participants with liver cirrhosis but without HCC at the time of biopsy were stained with a  $\gamma$ -OHPdG monoclonal antibody.  $\gamma$ -OHPdG levels were scored on a scale of 0-3 for distribution of positive stain, and again, 0-3 for intensity of positive stain. Sixty-two percent ( $n = 42$ ) had an IHC score of 2 or less, and 38% ( $n = 26$ ) had an IHC score of 3 or higher (Table 1).

[figure not shown]

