## 9. CORRELATIVE/SPECIAL STUDIES

### 9.1 Rationale for Methodology Selection

Our proposed study will assess whether our preclinical finding that Polyphenon E decreases the levels of  $\gamma$ -OHPdG holds true in the clinical setting. Our long term goal is to evaluate the role of  $\gamma$ -OHPdG as a predictive biomarker of HCC, and provide a novel prevention strategy for liver cancer, the third leading cause of cancer-related death globally, while expanding knowledge of the antioxidant effects of green tea polyphenols in the prevention of liver cancer.

To evaluate the change of  $\gamma$ -OHPdG in subjects treated with Polyphenon E, two methods will be used to measure the level of  $\gamma$ -OHPdG in liver tissue. First,  $\gamma$ -OHPdG levels in liver specimens will be determined by IHC, as previously described (34). Second, portions of the liver sample will be used for DNA isolation and further assay using LC/tandem MS methodology (for confirmation of  $\gamma$ -OHPdG antibody staining results by IHC) (34). The first method will provide rapid and semi-quantitative measurement of the  $\gamma$ -OHPdG level. The second method will provide quantitative and important confirmatory measurements of  $\gamma$ -OHPdG. IHC analysis is applicable in large-scale analysis of clinical samples, while LC/tandem MS methodology is costly and time consuming, but needed for validation of our IHC assay results. LC/tandem MS is suitable for small-scale sample analysis in a basic research laboratory. In this study, we propose to use LC/tandem MS methodology to confirm the findings from IHC analysis.

Blood and urine will be collected on Visit 1 for measuring bioactive catechin concentrations (EC, EGC, and EGCG) for pharmacokinetics study using a well-developed method (38). In our study, blood and urine samples will be collected in six subjects on day 1 of a 4 week cycle, prior to the first dose, and then at 1.5, 3.5, and 8.5 hours (+/- 5 minutes) after the first dose of Polyphenon E. Clearance of Polyphenon E will be compared among cirrhotic liver of participants in this study

and results from this population will be compared with non-cirrhotic historical control participants (38).

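### Section 13.4 claims power to confirm a fall of at least 30% in γ-OHPdG level, but the planned test against zero on a 0-6 semi-quantitative score can show only some fall in score

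*Combined protocol and SAP*

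**What the plan says.** Section 13.4 gives the planning expectation for γ-OHPdG expression after six months of treatment: "we expect a 30-40% decrease in" expression. It plans for 24 participants and says of that number: "This provides 80% or greater statistical power to confirm a 30% or bigger decrease in" γ-OHPdG "levels at a 0.05 alpha level with a two sided test". The analysis follows: "We will use a nonparametric Wilcoxon test to compare the post-pre differences to zero". The percentages become score points from an assumed pre-therapy average of 4: "about 1.33 and 1.60 after treatment = reduction of 33% and 40% respectively, down from 4". The power table in the same section sets Mean0 to 0, SD to 2 and N to 24, and gives power 0.84466 for 1.33 points and 0.94694 for 1.60.

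Section 13.5 says the IHC score runs from 0 to 6, with 0-2 called low and 3-6 high. Section 2.3.4 describes the earlier scoring: "levels were scored on a scale of 0-3 for distribution of positive stain, and again, 0-3 for intensity of positive stain". Section 9.1 says of IHC: "The first method will provide rapid and semi-quantitative measurement of the" γ-OHPdG level. It calls LC/tandem MS the quantitative, confirmatory method. LC-MS change is a secondary outcome (Sections 1.2.2, 8.2.2 and 13.5), summarised by mean and range per dose level with a trend test.

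Section 13.1 records that enrolment stopped early: 13 participants started treatment and 10 have biopsies both before and after it. Section 13.5 adapts the secondary and exploratory analyses to this. Section 13.4 adds a paragraph on safety and the MTD but leaves the IHC power claim as it was.

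**The concern.** Two different steps are run together in the power claim.

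- **Test.** Rejecting a null of zero shows that there was some fall. To confirm a fall of at least 30%, the confidence interval must exclude smaller falls. Nothing in Section 13.4 asks for that.
- **Scale.** The claim is about the level of the adduct, but the percent is a fraction of a semi-quantitative score. No section links a score step to an amount of adduct, and the percent changes with the starting score.

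At stake is how the biomarker result may be described. The claim as written lends a significant IHC comparison the authority of a confirmed 30% reduction in adduct, and Section 9.1 looks to these data to support a larger prevention study.

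**Working it through.** **Inputs (Section 13.4 unless stated).** N = 24; two-sided alpha 0.05; baseline mean 4; shifts 1.33 and 1.60; SD(B) = SD(A) = 2; correlation 0.5; null 0. Pairs obtained: 10 (Section 13.1). Everything below uses a normal-theory approximation with SD 2.

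**1. Reproduce the plan.** SD of the difference = √(4 + 4 − 2 × 0.5 × 2 × 2) = 2. The Wilcoxon efficiency for normal data is 3/π, so the effective N is 24 × 3/π = 22.9, taken as 22. Noncentral-t power with n = 22 and noncentrality (shift/2) × √22:

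| Shift | Share of 4 | Power, n = 22 | Unrounded 22.9 | Simulated signed-rank, N = 24 |
|---|---|---|---|---|
| 1.33 | 33% | 0.84466 | 0.860 | 0.864 |
| 1.60 | 40% | 0.94694 | 0.955 | 0.956 |
| 1.20 | 30% | 0.765 | 0.784 | 0.782 |

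The first two rows match the plan's table exactly, as power to reject zero. The table starts at 33%. At exactly 30% (0.30 × 4 = 1.2 points) the plan's own method gives 76.5%, below the claimed 80%. A plain t-test gives 80.4%, but it is not the planned test.

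**2. Where significance starts at N = 24.** t(0.975, 23) × 2/√24 = 0.84 points, 21% of 4. With n = 22, t(0.975, 21) × 2/√22 = 0.89 points, 22% of 4. At the 0.84 boundary the 95% CI runs from 0 to 1.69 points (0% to 42%). If the observed fall equals the planned 1.33, the CI is 0.49 to 2.17 points (12% to 54%). A true fall of only 20% (0.8 points) rejects zero in about 45% of trials.

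**3. What confirming 30% would take at N = 24.** The lower 95% limit must exceed 1.2 points, so the observed fall must be at least 1.2 + 0.84 = 2.04 points (51% of 4). The chance of that is the upper tail of a noncentral t with noncentrality ((true fall − 1.2)/2) × √24:

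- true 1.33: noncentrality 0.32, chance 4.9% (4.8% with the Wilcoxon efficiency)
- true 1.60: noncentrality 0.98, chance 15.4% (14.8%)

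**4. With the 10 pairs obtained.** Significance starts near t(0.975, 9) × 2/√10 = 1.43 points (36% of 4). Power against zero, with effective N = 10 × 3/π, is about 45% at 1.33 and 59% at 1.60. Excluding falls below 30% needs an observed 1.2 + 1.43 = 2.63 points (66% of 4).

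**5. The percent depends on the baseline score.** A 1.33-point fall is 44%, 33%, 27% or 22% of a baseline of 3, 4, 5 or 6. How that maps to adduct is unknown. As an assumption for illustration only, if one score step is a factor of 1.2, 1.5 or 2.0 in adduct, 1.33 points is a fall of 22%, 42% or 60%.

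**6. Internal consistency.** Section 13.4 also anticipates a post-therapy mean of 2. From 4, that is 2.0 points or 50%, which matches neither 33% nor 40%.

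**The case against.** The strongest reply is that nothing is hidden. The word in dispute sits in a power sentence, the next sentence names zero as the comparator, and the table prints Mean0 = 0. This is a phase I pilot, and Section 13.4 also frames the biomarker aim as exploratory. Section 13.5 asks for estimates with 95% CIs, under the exploratory endpoints, and LC-MS is already planned as a quantitative check. These points show that the remedy is close at hand. They do not give the design a property that it is said to have and lacks.

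Four stronger readings are tempting, and the documents do not support them:

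- **That the plan will report a 30-40% fall.** That range is a planning expectation, and no section prescribes reporting a significant result that way.
- **That the power arithmetic is wrong.** It reproduces to five decimals. The fault is in what it is said to show.
- **That the post-therapy mean of 2 undermines the power.** A shift of 2.0 at the same SD would have more power than 1.33 or 1.60. The mismatch is a drafting matter.
- **That a result from 21% upward would count as significant in the data in hand.** That threshold belongs to the planned 24 pairs. With 10 pairs it is about 36% of 4, although an estimate of that size still does not exclude a true fall below 30%.

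It is also only an inference, from the 0-6 range, that the two 0-3 grades are added. And the percentages of 4 used above are the plan's own metric, adopted to size the claim. They are not an endorsement of that metric.

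**Conclusion.** The point holds as a fault in the stated claim. A significant IHC comparison would show some fall in score. It would not confirm a fall of at least 30% in score, and still less in adduct. At the planned size the chance of a 95% CI that excludes falls below 30% is 5% to 15% at the plan's own effect sizes, against a claim of 80% or more. Even as power to reject zero, the 80% is not reached at exactly 30% under the planned test (76.5%, or 78% by simulation). With 10 pairs the gap is wider.

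These figures rest on SD 2, a baseline of 4 and approximately normal differences. Scores on a 0-6 scale will have ties, and a different SD would move the thresholds. That a zero null cannot confirm 30%, and that score percent is not adduct percent, depends on none of these assumptions.

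**What to change.** - In Section 13.4, restate the claim as power to detect a difference from zero of 1.33 points (84%) or 1.60 points (95%) at N = 24, and state that only 10 pairs were obtained.
- Report the IHC result as a score-point shift with its 95% CI (a Hodges-Lehmann estimate suits the Wilcoxon test), together with the number moving from 3 or more to 2 or less, which is the plan's own cut.
- Take any percent-decrease statement from the paired LC-MS post/pre ratio with its CI, and claim 30% or more only if the CI excludes smaller falls. State how many pairs have LC-MS at both times, because Section 10.2 has archival baseline tissue sent as a paraffin block.
- Reconcile the anticipated post-therapy mean of 2 with the 33% and 40% figures.

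The cost is rewording and one added LC-MS summary, with no new data collection. The price is a more modest headline claim.
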